9.7 Safety – Adverse Events

Adverse events will be coded using MedDRA. Treatment-emergent adverse events^g will be summarised by System Organ Class (SOC) and Preferred Term (PT).

^g A treatment-emergent adverse event is any adverse event occurring after start of IMP and until the last scheduled visit (or alternatively at a separate end-of-trial visit within 7 days of the last scheduled trial visit), or a pre-treatment adverse event or pre-existing medical condition that worsens in intensity after start of IMP and until the end-of-trial visit.

Adverse events and other safety assessments will be evaluated using descriptive statistics. For OHSS, see Section [9.6.3](#).

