The most frequently reported adverse drug reactions during treatment with FE 999049 are headache, pelvic discomfort, ovarian hyperstimulation syndrome (OHSS), pelvic pain, nausea, adnexa uteri pain and fatigue.¹ OHSS is an intrinsic risk of the ovarian stimulation. Known gastrointestinal symptoms associated with OHSS include abdominal pain, discomfort, and distension, nausea, vomiting, and diarrhoea. Ovarian torsion and thromboembolic events are known to be rare complications of ovarian stimulation treatment.

GONAL-F is a commercially available rFSH preparation with established safety and efficacy. The most frequent adverse events in relation to use of GONAL-F are as follows: headache, ovarian cysts and injection site reactions (all reported as very common, i.e. $\geq 10\%$) and abdominal pain, abdominal distension, abdominal discomfort, nausea, vomiting, diarrhoea and mild or moderate OHSS including associated symptomatology (all reported as common, i.e. 1% to $< 10\%$).²⁰ The GONAL-F dosing regimen used in this trial is in line with labelling recommendations.

The most serious risk associated with gonadotropin treatment is OHSS. OHSS manifests itself with increasing degrees of severity. Moderate / severe OHSS is associated with marked ovarian enlargement, fluid accumulation and other complications. In patients treated with a GnRH agonist protocol, early OHSS can be prevented by withholding gonadotropins or withholding human chorionic gonadotropin (hCG). Very rare cases of serious allergic reactions have been reported after injection of gonadotropins.

Trial Procedures and Concomitant Fertility Medications

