a) A minimum of 10 days with GnRH agonist administration should be ensured prior to confirmation of downregulation, which is defined as fulfilling the following criteria: 1) menstrual bleeding, 2) shed endometrium with a thickness <5 mm observed by transvaginal ultrasound, and 3) no ovarian follicles ≥ 10 mm (including cysts that cannot be punctured prior to stimulation) observed by transvaginal ultrasound. Subsequent visit(s) for confirmation of downregulation may be scheduled according to local practice. If downregulation is not achieved after 28 days, treatment with GnRH agonist will be stopped and the subject will be discontinued from the trial. If downregulation is confirmed, the subject may proceed to controlled ovarian stimulation and undergo the stimulation day 1 assessments on the same day.

b) Visits must be scheduled at least every second day; when the leading follicle reaches a diameter of ≥ 15 mm visits must be scheduled daily.

c) End-of-trial assessments must be performed at the subject's last scheduled visit (or alternatively at a separate end-of-trial visit within 7 days of the last scheduled trial visit). For subjects who undergo triggering of final follicular maturation, the end-of-trial visit must take place at least 9 days after triggering to cover the assessment of early OHSS (onset ≤ 9 days after triggering).

d) To be performed before randomisation to treatment.

e) If the subject has not experienced menstrual bleeding at the first assessment of confirmation of downregulation, a urinary pregnancy test is to be performed.

f) Subjects will start pituitary downregulation with GnRH agonist (triptorelin acetate, DECAPEPTYL) 0.1 mg/day subcutaneously in the mid-luteal phase (i.e. cycle day 21-24) of their menstrual cycle.

g) Abdominal or transvaginal ultrasound.

h) Screening: AMH, TSH, and prolactin; stimulation day 1 (before randomisation to treatment and administration of the first IMP dose), stimulation day 6 and end-of-stimulation: estradiol and progesterone.

i) CHEM-20 and CBC

j) In case achievement of downregulation is doubtful or it is deemed helpful, estradiol is to be measured (<50 pg/mL or 180 pmol/L).

k) Once downregulation is confirmed, randomisation and start of stimulation must occur within 7 days. Randomisation will be stratified according to the investigator's assessment of an appropriate starting dose (10 µg FE 999049 / 150 IU GONAL-F or 15 µg FE 999049 / 225 IU GONAL-F).

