6.5.4 End-of-stimulation

The end-of-stimulation visit must take place when the subject reaches the criterion for triggering of final follicular maturation or any of the cycle cancellation criteria because of poor or excessive follicular development as specified in [Table 6-2](#). Administration of hCG must take place as soon as reaching the criterion for triggering of final follicular maturation.

If triggering as soon as reaching the criterion would lead to oocyte retrieval or embryo transfer on a day the clinic is closed e.g. Sunday or a public holiday, stimulation may be continued for one additional day, meaning triggering is delayed for a maximum of one day.

Table 6-2 Triggering and Cycle Cancellation Criteria related to Follicular Development

Poor follicular development	Triggering criterion ^{a)}	Excessive follicular development
If it is judged by the investigator that the triggering criterion cannot be reached by day 20, the cycle is cancelled.	≥ 3 follicles with a diameter ≥ 17 mm. 1 or 2 follicles with a diameter ≥ 17 mm and investigator judgement that ≥ 3 follicles with a diameter ≥ 17 mm cannot be reached and triggering is preferred instead of cycle cancellation. <25 follicles with a diameter ≥ 12 mm.	If ≥ 25 follicles with a diameter ≥ 12 mm, the cycle is cancelled.

a) The investigator has the option of cancelling cycles due to safety concerns. Administration of triggering drug must be performed the day the criterion is met or the day after.

The following must take place at end-of-stimulation visit:

- Transvaginal ultrasound of uterus and ovaries (endometrial thickness, endometrial triple-layer structure, endometrial echogenicity pattern, ovarian volume, number and size of follicles)
- Blood collection for central laboratory analysis of estradiol and progesterone – the blood sample must be drawn at least 8 hours after the latest administration of IMP and GnRH agonist
- Dispensing of hCG, as applicable
- Drug accountability of hCG and IMP
- Recording of use of any concomitant medication
- Recording of adverse events

For subjects with cycle cancellation, end-of-trial assessments (Section [6.12](#)) must take place at end-of-stimulation visit or, alternatively, at a separate end-of-trial visit within 7 days of the end-of-stimulation visit. For subjects who receive the triggering drug, the next visit is the oocyte retrieval visit which must be scheduled 36h (± 2 h) after the administration of hCG.

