6.8 Embryo Transfer

For subjects eligible to transfer, the transfer is performed on day 3 (embryo stage) after oocyte retrieval.

Subject-related procedures for embryo transfer:

- Transfer of 1 or 2 embryo(s) of the highest quality available. The decision to transfer either 1 or 2 embryos will be based on the subject's wishes and the investigator's recommendation and in accordance with local guidelines and/or regulations.
- Dispensing of progesterone for luteal phase support, if applicable

The following assessments must take place:

- Drug accountability of progesterone
- Recording of use of any concomitant medication
- Recording of adverse events

For subjects who undergo triggering of final follicular maturation with hCG and have ≥ 20 oocytes retrieved, no transfer of embryos will take place and end-of-trial assessments (Section 6.12) must take place at a separate end-of-trial visit scheduled at least 9 days after triggering. For subjects with embryo transfer, the next visit is the β hCG test visit which must be scheduled 13-15 days after transfer (Section 6.9).

6.9 β hCG test

Subjects who have undergone transfer must attend a visit 13-15 days after transfer.

The following procedures / assessments must take place:

- Blood collection for local laboratory analysis of β hCG
- Dispensing of progesterone for luteal phase support, if applicable
- Drug accountability of progesterone
- Recording of use of any concomitant medication
- Recording of adverse events

The β hCG test will be evaluated according to the laboratory's reference ranges. In case of a borderline β hCG result, the test should be repeated.

For subjects with a negative β hCG test, end-of-trial assessments as specified in Section 6.12 must take place at β hCG test visit or, alternatively, at a separate end-of-trial visit within 7 days of the β hCG test visit. For subjects with a positive β hCG test, the next visit is the clinical pregnancy visit 5-6 weeks after transfer (Section 6.10).

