6.12 End-of-trial

If a subject attends the scheduled trial visits, the end-of-trial assessments should take place at the last scheduled trial visit, i.e. for subjects with a confirmed vital pregnancy, the ongoing pregnancy visit would be the last scheduled trial visit and thus the visit where the end-of-trial assessments

should be done. Alternatively, a separate end-of-trial visit within 7 days of the last scheduled trial visit may be scheduled.

The following procedures / assessments must take place at the end-of-trial visit, irrespective of whether the subject discontinues the trial prematurely or completes it:

- Physical examination
- Gynaecological examination
- Recording of use of any concomitant medication
- Recording of adverse events
- Blood collection for central laboratory analysis of:
 - Clinical chemistry and haematology parameters

These assessments serve to document the subject's physical health at the end of the trial.

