8.5 Follow-up of Adverse Events and Serious Adverse Events

8.5.1 Follow-up of Adverse Events with Onset during the Trial

During the trial, the investigator must follow-up on each adverse event until the subject's last visit. After the subject's last visit, the investigator must follow-up on any adverse event classified as serious or considered to have a reasonable possible causality to the IMP until it is resolved or until the medical condition of the subject is stable. All such relevant follow-up information must be reported to Ferring. Follow-up should continue until the outcome of recovered, recovered with sequelae, or fatal, has been reached. If the event is considered stable or a chronic condition, the investigator and Ferring may agree that further follow-up is not required.

8.5.2 Collection of Serious Adverse Events with Onset after Last Visit in the Trial

If an investigator becomes aware of an SAE after the subject's last visit, diagnosed either to the subject herself or to the fetus / neonate, and investigator assesses the SAE to have a reasonable possible causality to IMP (FE 999049 or GONAL-F) or NIMP where Ferring is Marketing Authorisation Holder (DECAPEPTYL), the case will have to be reported to Ferring (see

Section 8.4.2), regardless how long after the end of the trial this takes place.

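### Treatment-emergent adverse events are counted to each woman's last visit, whose timing depends on response and outcome, so crude incidences by arm also reflect transfer and pregnancy rates

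*Combined protocol and SAP*

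**What the plan says.** Section 9.7 (footnote g) counts as treatment-emergent "any adverse event occurring after start of IMP and until the last scheduled visit", or until a separate end-of-trial visit up to 7 days later. It also counts earlier conditions that worsen in that period. The analysis plan is brief: "Adverse events and other safety assessments will be evaluated using descriptive statistics", with tables by system organ class and preferred term. Section 9.7 gives no common cut-off, split by phase or person-time.

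The end of this window depends on how the cycle went:

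- **Cancelled cycle (Section 6.5.4):** at end-of-stimulation, or "at a separate end-of-trial visit within 7 days of the end-of-stimulation visit".
- **Any triggered woman (Table 6-1, footnote c):** "the end-of-trial visit must take place at least 9 days after triggering to cover the assessment of early OHSS".
- **20 or more oocytes, so no transfer (Section 6.8):** the end-of-trial assessments "must take place at a separate end-of-trial visit scheduled at least 9 days after triggering".
- **Negative βhCG test (Section 6.9):** 13-15 days after transfer, or up to 7 days later.
- **Positive test without vital pregnancy (Section 6.10):** 35-48 days after transfer.
- **Vital pregnancy (Sections 6.11 and 6.12):** 70-83 days after transfer, since "for subjects with a confirmed vital pregnancy, the ongoing pregnancy visit would be the last scheduled trial visit".

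Section 6.12 also allows, in general terms, a separate visit within 7 days of the last scheduled one. For a serious event after the last visit that the investigator judges related, Section 8.5.2 says "the case will have to be reported to Ferring", with no time limit.

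**The concern.** Comparing the safety profiles of the two products is a secondary objective (Section 2.1). Both products are given for at most 20 days, but the period in which an event can count varies several-fold between women, and it varies with things the products may affect. Retrieval of 20 or more oocytes bars transfer, and 25 or more follicles of at least 12 mm cancels the cycle. An arm with a stronger response may therefore have more women with short windows. An arm with more pregnancies has more women with weeks of luteal support and first-trimester complaints in their count.

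Some of those complaints are hard to tell from drug reactions. The reactions listed for FE 999049 in Section 1.3 include headache and "pelvic pain, nausea, adnexa uteri pain and fatigue". Two products with identical effects during stimulation could thus show different incidences, and the arm with fewer transfers or pregnancies would look better tolerated.

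**Working it through.** The plan gives no computed figure for the adverse-event window, so there is none to reproduce. Two checks follow.

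**1. Length of the window after triggering**

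Inputs: retrieval 36 ± 2 h after triggering (Section 6.6), transfer 3 days after retrieval (Section 6.8), and the visit windows listed above.

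Transfer falls 34/24 + 3 = 4.42 to 38/24 + 3 = 4.58 days after triggering. Adding the visit windows gives:

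| Course | Sum (days) | Last visit | With optional 7 days |
|---|---|---|---|
| Triggered, no transfer | at least 9 | at least 9 | no maximum in Section 6.8 |
| Negative test | 4.42 + 13 to 4.58 + 15 | 17.4-19.6 | up to 26.6 |
| No vital pregnancy | 4.42 + 35 to 4.58 + 48 | 39.4-52.6 | up to 59.6 |
| Vital pregnancy | 4.42 + 70 to 4.58 + 83 | 74.4-87.6 | up to 94.6 |

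Cancelled cycles have no trigger and close 0-7 days after end-of-stimulation. A vital pregnancy gives 74.4/9 = 8.3 to 87.6/9 = 9.7 times the 9-day minimum.

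**2. Effect on crude incidence when the products do not differ**

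All rates here are assumptions; none is in the documents. Stimulation lasts 10 days and the same constant daily hazard *h* applies in both arms. Windows from start of IMP, at mid-range, are 13.5 days (cancelled), 19 (no transfer), 28.5 (negative test), 56 (no vital pregnancy) and 91 (ongoing pregnancy).

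Reference arm: 5% cancelled, 25% no transfer, 35% negative, 5% no vital pregnancy, 30% ongoing. Mean window = 0.05×13.5 + 0.25×19 + 0.35×28.5 + 0.05×56 + 0.30×91 = 45.5 days.

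Crude incidence = Σ share × (1 − exp(−*h* × window)).

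| Other arm | Mean window (days) | Deficit at *h* = 0.001 | 0.005 | 0.01 | 0.02 |
|---|---|---|---|---|---|
| Same rates | 45.5 | 0.0 | 0.0 | 0.0 | 0.0 |
| Pregnancy 5 points lower | 42.4 | 0.3 | 1.2 | 1.7 | 2.0 |
| Pregnancy 10 points lower | 39.2 | 0.6 | 2.3 | 3.5 | 4.0 |
| Transfer 20 and pregnancy 10 points lower | 37.4 | 0.8 | 3.2 | 5.0 | 6.4 |

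Deficits are in percentage points. At *h* = 0.01, for example, the reference arm has 33.7% and the arm with pregnancy 10 points lower has 30.2%.

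A second form lets the excess come from pregnancy itself. Take a 20% risk during stimulation in both arms, and a first-trimester event in half of ongoing pregnancies. Incidence = 1 − (1 − 0.20)(1 − 0.5*p*). With *p* = 35%, 30% and 25% this gives 34%, 32% and 30%. A 10-point difference in pregnancy shifts incidence by 4 points, and a 5-point difference by 2.

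With a cut-off 9 days after triggering, every triggered woman has 19 days in the first model. Incidence at *h* = 0.01 is 0.05 × (1 − e^−0.135) + 0.95 × (1 − e^−0.19) = 0.6% + 16.4% = about 17.1% in each arm. Transfer and pregnancy no longer enter; only a difference in cancellation rates would.

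**The case against.** Counting every event to the end of participation is a legitimate whole-trial summary, and the safety analyses are descriptive. The distortion needs a difference in transfer or pregnancy rates, and neither the differences used above nor the event rates come from the documents. With 150 women per arm, the 95% confidence interval around 34% against 30% is 1.96 × √[(0.34×0.66 + 0.30×0.70)/150] = ±10.5 points, so a shift of 2 to 4 points lies well inside chance variation. The most serious risk, OHSS, is already reported as early and late at the 9-day mark (Sections 7.2.12 and 9.6.3). Section 9.6.1 defers detail to a separate SAP, whose text is not among the documents and which may define phases.

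Most of this stands and limits the size of the point. It does not remove it: the definition on record is footnote g, a descriptive table is still read across arms, and a systematic shift is not excused because chance variation is larger.

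Two stronger readings are tempting, and the documents do not support them. A reader might infer that related serious events after the last visit are lost. They are not: Section 8.5.2 requires them to be reported without time limit, Section 8.4.1 records listed pregnancy and neonatal events as serious, and Section 13.1 puts follow-up data in a report addendum. The gap is only that Section 9.7 does not say where related events reported under 8.5.2 will be shown. A reader might also take 9 days as the closing time without transfer. It is a minimum, and cancelled cycles can close sooner.

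**Conclusion.** The point holds for the crude between-arm incidences in Section 9.7. Window length follows from response and outcome and differs about 8- to 10-fold between the 9-day minimum and a vital pregnancy. The resulting distortion is zero if transfer and pregnancy rates match. In the constant-hazard illustration it is about 0.3-2 points for a 5-point difference in ongoing pregnancy, about 0.6-4 points for a 10-point difference, and up to 6.4 points if transfer is also 20 points lower. These sizes rest on the assumed shares and hazards above. Events specific to the luteal phase or early pregnancy would be affected most.

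The primary non-inferiority analysis is untouched. This is a modest weakness in a secondary comparison that is cheap to repair; it does not show that the planned safety comparison will mislead.

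**What to change.** Keep the present table and footnote g, and add the following to Section 9.7:

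1. A between-arm summary of events with onset from start of IMP to 9 days after triggering. For untriggered women it runs to the end-of-trial visit, with a statement that the schedule guarantees them only 0-7 days after end-of-stimulation. Some imbalance therefore remains if cancellation rates differ. Late OHSS falls outside this window and stays in the existing OHSS tables and the to-last-visit table.
2. Events per person-time beside the to-last-visit table. These adjust for length of observation but not for the different kinds of event in early pregnancy, so they do not replace the first item.
3. A separate listing, by arm, of related serious events reported under Section 8.5.2 with onset after the last visit, with maternal events apart from fetal and neonatal ones. Footnote g should not be widened to take these in: their collection is open-ended and filtered by causality, and it includes events in the fetus or neonate.

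Section 8.2.1 counts the 9 days from the end-of-stimulation visit, while Sections 6.1, 6.6 and 6.8 count from triggering. These must be reconciled, because triggering may fall a day after the criterion is met.

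Onset dates are already recorded (Section 8.2.2), so no new data are needed. The cost is protocol and SAP wording, one more set of tables, and two windows to explain in the report.

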9.8 Pregnancy Follow-up

Live birth will be compared between FE 999049 and GONAL-F using the same method as for pregnancy endpoints. Follow-up data on neonatal health will be described. These data will be reported separately.

10 DATA HANDLING

10.1 Source Data and Source Documents

Source Data – ICH Definition

Source data are defined as all information in original records and certified copies of original records of clinical findings, observations, or other activities in a clinical trial necessary for the reconstruction and evaluation of the trial. Source data are contained in source documents (original records or certified copies).

Source Documents – ICH Definition

Source documents are defined as original documents, data, and records (e.g. hospital records, clinical and office charts, laboratory notes, memoranda, subjects' diaries or evaluation checklists, pharmacy dispensing records, recorded data from automated instruments, copies or transcriptions certified after verification as being accurate copies, microfiches, photographic negatives, microfilm or magnetic media, x-rays, subject files, and records kept at the pharmacy, at the laboratories and at medico-technical departments involved in the clinical trial).

Trial-specific Source Data Requirements – Ferring

Source documents need to be preserved for the maximum period of time permitted by local requirements. For each subject included in the trial, the investigator will record and retain source documents containing at least the following information, if applicable:

- Existence of subject (name, date of birth)
- Confirmation of participation in trial (trial ID, subject ID)
- Informed consent (date and time of oral information, date and time of handing out informed consent forms, date and time of obtaining written informed consents)
- Eligibility for participation in the trial (documenting all inclusion / exclusion criteria)
- Relevant medical and infertility history
- Body weight and height measurements
- Visit dates
- Any assessment performed, e.g. physical examination
- Dates and daily doses of IMP
- Dates and daily doses of NIMPs
- Dates and daily doses of concomitant medication
- Date of oocyte retrieval and number of oocytes retrieved
- Date of transfer and number and quality of embryos transferred
- Dates and results of β hCG test and ultrasound at clinical and ongoing pregnancy visits

- Adverse events (description as well as start/stop date and time)
- OHSS symptoms, preventive intervention (i.e. cycle cancellation), investigations and treatments
- Reason for discontinuation
- Event of unblinding, including the reason for unblinding
- Pregnancy outcome, i.e. live birth or pregnancy loss, and neonatal health at birth and 4 weeks after birth

No specific protocol data can be recorded directly in the EDC system without prior written or electronic record. The source of the various data will be described in a source agreement signed by the investigator and retained in the site file.

If the trial sites use electronic subject record systems, the sponsor will decide if the electronic subject records qualify for the trial and document the decision. If the electronic subject records system does not qualify for the trial, it may be considered to utilise certified printouts of the data in the electronic subject records system for source data as an exception.

The source data for the endocrine parameters will be available at the central laboratory.

